6.14.1. Extent of Exposure

Exposure will be reported for patients in the Modified Safety Population. Exposure to lebrikizumab from the patient's parent study and from Study KGAA will be combined for reporting the extent of exposure in an integrated analysis. For Study KGAA, only exposure in Study KGAA will be reported. Exposure will be reported for lebrikizumab 250 mg Q2W, lebrikizumab 250 mg Q4W, and lebrikizumab 250 mg overall. Drug interruption time period due to the use of long-term systemic rescue therapies will not be removed from study drug exposure calculations as described in compound level safety standards.

The duration of exposure in Study KGAA will be calculated as:

Duration of exposure (days)

= max [Date of KGAA last visit (scheduled or unscheduled) in the Treatment Period,

 $Date\ of\ last\ dose$ | $-Date\ of\ KGAA\ first\ dose + 1$

While Study KGAA is still ongoing, before its final lock, there are patients who may have home injections after their last clinical visit, so the maximum date of the last dose and last visit will be used.

Total exposure to lebrikizumab 250 mg Q2W, total exposure to lebrikizumab 250 mg Q4W, and total exposure to lebrikizumab 250 mg overall will be summarized, by number and percentage of patients, using the following categories:

- >0, ≥7 days, ≥14 days, ≥30 days, ≥60 days, ≥90 days, >112 days, ≥120 days, ≥150 days, ≥183 days, ≥210 days, and ≥273 days, ≥365 days (1 year), ≥548 days, ≥730 days (2 years). Note that patients may be included in more than 1 category.
- >0 to <7 days, ≥7 to <14 days, ≥14 to <30 days, ≥30 to <60 days, ≥60 to <90 days, ≥90 to <120 days, ≥120 to <150 days, ≥150 to <183 days, ≥183 to <210 days, ≥210 to <273 days, ≥273 to <365 days, ≥365 days to <548 days, ≥548 days to <730 days, ≥730 days.

Additional exposure ranges may be considered if necessary.

The summaries will also include the following information:

• Total exposure in patient years, calculated as:

Total exposure in patient years $= \frac{Sum \ of \ duration \ of \ exposures \ for \ all \ patients \ in \ treatment \ group}{sum \ of \ duration \ of \ exposures \ for \ all \ patients \ in \ treatment \ group}$

- Mean and median total dose. Total dose (in mg) is calculated by the number of active injections taken multiplied by 250 mg.
- Total number of injections received will be derived from the *Study Drug Administration* eCRF and the information from the Dosing Diary.

6.14.2. Immunogenicity

The analyses of immunogenicity will be processed with parent studies' data together in an integrated database. More details are specified in Program Safety Analysis Plan (PSAP). No Study KGAA-specific immunogenicity analyses will be conducted.

6.14.2.1. Analysis Sets

Patients may transition from one of the parent studies or enroll directly into Study KGAA without being first enrolled in other studies. Immunogenicity analyses will be focused on patients who received at least one injection of lebrikizumab and have been monitored for at least 26 weeks since the day of the first exposure. This comprises of patients from Studies KGAB/AD04, KGAC/AD05, KGAD/AD06, KGAA/AD07 (direct entry patients), KGAE/AD17, KGAK/AD18, including those who discontinued before enrolling in Study KGAA.

For patients who are assigned to lebrikizumab either in parent Study or KGAA and receive at least 1 dose of the study drug and are treatment-emergent (TE) antidrug antibody (ADA) evaluable, the incidence rates of TE ADA status and maximum titer distributions are tabulated. This analysis will utilize the Atopic Dermatitis All Lebrikizumab Exposure Integrated Immunogenicity Analysis Set with New Immunogenicity Assay and will include no-drug follow-up period.

Table KGAA.6.8 summarizes the immunogenicity analysis set.

Table KGAA.6.8. Immunogenicity Analysis Set

Analysis Set	Population	Description	Baseline	Post Baseline Period
Atopic Dermatitis	Modified Safety	Patients who received at least	See	Postbaseline includes all
All Lebrikizumab	Population (see	one injection of lebrikizumab	Section 6.1.2	observations after the day of
Exposure	Table KGAA.6.1)	and have been monitored for		first dose of the analysis
Integrated		at least 26 weeks. This		period and before the end of
Immunogenicity		comprises patients from		KGAA Main study, or to the
Analysis Set with		studies KGAB/AD04,		end of the parent study in
New		KGAC/AD05, KGAD/AD06,		case participant discontinued
Immunogenicity		KGAA/AD07 (direct entry		before entering KGAA Main.
Assay (KGAB,		patients), KGAE/AD17,		
KGAC, KGAD,		KGAK/AD18, including		
KGAA, KGAE,		those who discontinued		
KGAK)		before enrolling in Study		
		KGAA.		

6.14.2.2. Analyses

The number and proportion of patients who are TE ADA+ will be tabulated for the overall lebrikizumab treated patients, where proportions are relative to the number of patients who are TE ADA evaluable. The tabulation will include the number and proportion of patients with ADAs Present at baseline and the number and proportion of TE ADA+ patients exhibiting neutralizing antibodies (NAb). Analysis will be conducted for all patients, and those aged 12 to under 18.

The baseline ADA, along with the baseline titer distribution for individuals with ADA Present at baseline, and the distribution of postbaseline maximum titers for TE ADA+ patients, will be presented.

Table KGAA.6.9 provides the list of planned core immunogenicity analyses.

KGAA, KGAE,

KGAK)

Characterization of

Distribution.

Analysis	Details	Analysis Set
Incidence of Antidrug	Within the patients evaluable for TE ADA, the number and	Atopic Dermatitis
Antibodies and Neutralizing	percentage of patients with the following will be summarized:	All Lebrikizumab
Antibodies	Patients evaluable for TE ADA	Exposure
	ADA Present at baseline and NAb Present at baseline,	Integrated
	TE ADA+, TE ADA Inconclusive, and TE ADA-,	Immunogenicity
	Treatment-induced TE ADA+ and treatment-boosted TE	Analysis Set with
	ADA+,	New
	TE ADA+ with NAb Present postbaseline, and	Immunogenicity
	TE ADA+ without NAb Present postbaseline, but having NAb	Assay (KGAB,
	Inconclusive at the follow up visit.	KGAC, KGAD,

The distribution of the maximum titer values for the

Table KGAA.6.9. List of Core Immunogenicity Analyses

Abbreviations: ADA = antidrug antibodies; Nab = neutralizing antibodies; TE = treatment-emergent.

6.15. Subgroup Analyses

6.15.1. Efficacy Subgroup Analyses

Postbaseline Maximum Titer TE ADA+ patients will be summarized.

Subgroup analyses will be conducted for the secondary endpoints, the proportion of patients achieving an IGA of 0 or 1, and the proportion achieving EASI-75 across the treatment period in the mITT population.

The following subgroups will be analyzed:

- Age group (adolescents [from 12 up to 18], adults 18 and over)
- Sex (male, female)
- Region (US, EU, Rest of World)

Some additional subgroup analyses may be added to meet regulatory requirements. The analysis of additional subgroups will not require an amendment to the SAP.

6.15.2. Safety Subgroup Analyses

Subgroup analysis for safety related endpoints will be performed within the context of the integrated safety analysis.

6.16. Protocol Deviations

Protocol deviations will be identified throughout the study. Important protocol deviations are defined as those deviations from the protocol likely to have a significant impact on the completeness, accuracy, and/or reliability of the study data or that may significantly affect a patient's rights, safety, or wellbeing.

Potential examples of important protocol deviations include patients who violated the inclusion and exclusion criteria, used an interfering concomitant medication, and significant non-compliance with study medication (under 75% of expected injections). Refer to a separate

document called "KGAA Trial Issues Management Plan" for the important protocol deviations with categorizations.

The number and percentage of patients having important protocol deviations will be summarized within category and subcategory of deviation by treatment group using the ITT population.

A by-patient listing of important protocol deviations will be provided.

6.16.1. Impact of COVID-19

Impact of pandemic (for example, COVID-19 [coronavirus disease 2019]) on analyses will be systemically addressed prior to study unblinding at submission database lock (DBL), once the impact on the study conduct are fully understood. A summary or listing may be provided to summarize missing visits due to COVID-19.

6.18. Interim Analyses and Data Monitoring

Data Monitoring Committee/Data Safety Monitoring Board (DMC/DSMB): The lebrikizumab Phase 3 AD programs' DSMB is an independent expert advisory group commissioned and charged with the responsibility of evaluating cumulative safety at regular intervals, as well as on an ad hoc basis, as needed. The DSMB will consist of members external to Lilly and follow the rules defined in the DSMB charter, focusing on potential and identified risks for this molecule. Data Monitoring Committee membership will include, at a minimum, a physician with expertise in dermatology and a statistician. No member of the DSMB may have contact with study sites. This committee will make recommendations as to a) continue the clinical studies without modification; b) continue the clinical studies with modifications; or c) terminate one or more of the clinical studies. Details outlining the roles and responsibilities of the DSMB are documented in the "Dermira DRM06 DSMB Program Charter" and the planned analyses are outlined in the DSMB analysis plan prior to the first unblinded assessment.

Access to the unblinded safety data will be limited to the DSMB. The study team will not have access to the unblinded data. Only the DSMB is authorized to evaluate unblinded data. The

purpose of the DSMB is to advise Lilly regarding patient safety; however, the DSMB may request key efficacy data to put safety observations into context and to confirm a reasonable benefit/risk profile for ongoing patients in the study.

A small group could be unblinded including but not limited to global patient safety, medical, statistics, data management, regulatory, etc. who do not have direct interaction with the sites to prepare for regulatory interactions, safety updates, and disclosures if needed, while another team remains blinded to carry the day to day study work. The regulatory submission and related preparation will include DSMB #5, Submission interim, 4 Month Safety Update, and test transfers between DSMB #5 and KGAK/AD18 Week 16 DBL. Treatment, dispense, PK, and ADA information of patients enrolled from the KGAK/AD18 study will keep blinded until KGAK/AD18 study unblinded. A separate unblinding plan will provide a detailed rationale and procedure for unblinding to maintain the integrity of the study.

Submission DBL: An unblinded interim analysis will be performed to support regulatory submissions when it is estimated the regulatory requirement for safety exposure for the lebrikizumab program is met. Only the non-KGAK patients will be unblinded. This DBL will include all data collected by the cut-off date except the data from KGAK patients.

Week 100 DBL: Another unblinded interim analysis will be performed at the time (that is, a cut-off date) the last patient completes Week 100, or the early termination visit from the study. This DBL will include all data collected by the cut-off date and is the final analysis for the efficacy endpoints up to Week 100.

Final DBL: A final DBL will occur after all patients have completed the safety follow-up period of the study or discontinued from the study.

Additional interim analyses may also be performed for regulatory interactions, safety updates, and disclosures.

6.19. Annual Report Analyses

Based on regulatory requirements for the Development Safety Update Report (DSUR), reports will be produced (if not already available from the study CSR) for the reporting period covered by the DSUR.

6.20. Clinical Trial Registry Analyses

Additional analyses will be performed (if not already available from the study CSR) to fulfill the Clinical Trial Registry (CTR) requirements.

Analyses provided for the CTR requirements include the following:

Summary of AEs, provided as a dataset, will be converted to an XML file. Both SAEs and 'Other' AEs are summarized: by treatment group, by MedDRA PT.

• An AE is considered 'Serious' whether or not it is a TEAE.

- An AE is considered in the 'Other' category if it is both a TEAE and is not serious. For each SAE and 'Other' AE, for each term and treatment group, the following are provided:
 - o the number of patients at risk of an event,
 - o the number of patients who experienced each event term, and
 - o the number of events experienced.
- Consistent with www.ClinicalTrials.gov requirements, 'Other' AEs that occur in fewer than 5% of patients/subjects in every treatment group may not be included if a 5% threshold is chosen (5% is the minimum threshold).
- AE reporting is consistent with other document disclosures, for example, the CSR, manuscripts, and so forth.

7. Unblinding Plan

Unblinding details are specified in a separate unblinding plan.

8. References

- [CDC] Centers for Disease Control and Prevention. Growth Chart Training resources page. Accessed June 09, 2020. https://www.cdc.gov/nccdphp/dnpao/growthcharts/resources/sas.htm
- PhUSE resources page. Analyses and Displays Associated with Measures of Central Tendency Focus on Vital Sign, Electrocardiogram, and Laboratory Analyte Measurements in Phase 2-4 Clinical Trials and Integrated Submission Documents. 2013. Accessed June 09, 2020. http://www.phusewiki.org/docs/CSS%20White%20Papers%202016/CSS_WhitePaper_Central Tendency v1.0.pdf
- PhUSE resources page. Analyses and Displays Associated with Outliers or Shifts from Normal to Abnormal Focus on Vital Sign, Electrocardiogram, and Laboratory Analyte Measurements in Phase 2-4 Clinical Trials and Integrated Submission Documents. 2015. Accessed June 09, 2020. http://www.phusewiki.org/docs/CSS%20White%20Papers%202016/CS_WhitePaper_Outliers Shifts_v1.0.pdf

Appendix 1. Study Visit Mapping for Pruritus NRS, Sleeploss, POEM, and Skin-Pain NRS Diary

Pruritus NRS, Skin Pain NRS, and Sleep-loss score are collected as a daily diary, entries will be mapped to study week by the following:

Week	Start Day	End Day
Week 0	Date of First Injection – 7	Date of First Injection – 1
Week 2	Week 2 Visit Date – 7	Week 2 Visit Date – 1
Week 4	Week 4 Visit Date – 7	Week 4 Visit Date – 1
Week 16	Week 16 Visit Date – 7	Week 16 Visit Date – 1
Week 28	Week 28 Visit Date – 7	Week 28 Visit Date – 1
Week 40	Week 40 Visit Date – 7	Week 40 Visit Date – 1
Week 52	Week 52 Visit Date – 7	Week 52 Visit Date – 1

Note: If the date of the first injection is missing, the randomization date will be used.

If multiple assessments on a single day are present, use the first assessment. If at least 1 of the 7 days contains nonmissing daily assessments, the postbaseline weekly score will be calculated using a prorated weekly average. If the range of 7 days are all missing daily assessments, then the weekly score is missing.

The POEM is collected every week via eDiary until Week 52 visit, the visit week mapping will follow the following rule: the last collected POEM data before the visit date would be used, the evaluation window is injection date -7 to injection date -1 for baseline, and visit date -7 to visit date -1 for post-baseline. For example, if a patient gets an injection on the 14^{th} , we would use the scale completed between the 13^{th} and the 7^{th} .

Appendix 2. Definition of Rescue Medications

The following topical treatments and systemic treatments are defined as:

1. Topical Atopic Dermatitis Treatment (including TCS, TCI, and crisaborole)

Route of topical treatments includes: Topical and Transdermal.

Topical Corticosteroids (TCS): ATC code is D07

High Potency TCS: ATC codes: D07AC or D07AD

Low or moderate potency TCS: ATC code is D07, excluding D07AC or D07AD

Topical calcineurin inhibitor (TCI): Preferred Term includes: TACROLIMUS, PIMECROLIMUS

Crisaborole: Preferred Term includes: CRISABOROLE

2. Systemic Atopic Dermatitis Treatment (including systemic corticosteroids, immunosuppressants, biologics, and phototherapy/photochemotherapy)

Route of systemic treatments administration includes: Oral, Intra-Arterial, Intramuscular, Intraperitoneal, Intravenous, Subcutaneous, and Transdermal. (This condition applies to the following categories except for phototherapies.)

Systemic Corticosteroids: ATC code is H02

Immunosuppressant: Defined as: ATC2 is L04 or Preferred terms of Abrocitinib or Ruxolitinib excluding Preferred terms mentioned in Biologics

Biologics: Defined as following preferred terms:

Infliximab, Infliximabum, Etanercept, Etanerceptum, Adalimumab, Adalimumabum, Certolizumab, Certolizumabum, Certolizumab pegol, Golimumab, Golimumabum, Ozoralizumab, Afelimomab, Afelimomabum, Tumor Necrosis Factor Alpha (TNF-) Inhibitors, Tabalumab, Tregalizumab, Anakinra, Basiliximab, Basiliximabum, Daclizumab, Daclizumabum, Tocilizumab, Tocilizumabum, Mepolizumab, Mepolizumabum, Rilonacept, Rilonaceptum, Ustekinumab, Canakinumab, Briakinumab, Fezakinumab, Sirukumab, Sarilumab, Lebrikizumab, Secukinumab, Olokizumab, Gevokizumab, Brodalumab, Ladarixin, Ixekizumab, Dupilumab, Tildrakizumab, Tildrakizumabum, Reslizumab, Reslizumabum, Guselkumab, Guselkumabum, Olamkicept, Fletikumab, Bimekizumab, Mirikizumab, Risankizumab, Abatacept, Ligelizumab, Vedolizumab, Belimumab, Nemolizumab, Tralokinumab, Omalizumab

Phototherapy or Photochemotherapy:

Programming search of medication name (actual term or preferred term) contains 'photo', then medical to manually review to confirm whether the medication in question is indeed 'Phototherapy' or 'Photochemotherapy'

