The following efficacy assessments will be summarized at each visit they are collected:

- Change and percent change from baseline in EASI score at each visit
- Proportion of patients with EASI-50 and EASI-90 scores at each visit
- Percentage of patients with a Pruritus NRS of ≥ 4 points at baseline who achieve a ≥4 points reduction from baseline in the Pruritus NRS score at prespecified time points (for studies in which these data were collected)
- Percentage change from baseline in Pruritus NRS score at prespecified time points (for studies in which these data were collected)
- Percentage of patients with a Sleep-loss score ≥2 points at baseline who achieve a ≥2 points reduction from baseline in the Sleep-loss score at prespecified time points (for studies in which these data were collected)
- Change from baseline in sleep-loss at prespecified time points (for studies in which these data were collected)
- Percentage of patients with a Skin-pain NRS ≥ 4 points at baseline who achieve a ≥ 4 points reduction from baseline in the Skin-pain NRS at prespecified time points (for studies in which these data were collected)
- Change from baseline in Skin-pain NRS at prespecified time points (for studies in which these data were collected)
- Change from baseline in POEM scores at prespecified time points through the end of study (for studies in which these data were collected)
- Change from baseline in BSA at prespecified time points through the end of study
- Proportion of patients requiring AD concomitant treatment by visit
- Proportion of TCS/TCI free days from baseline by visit (for studies in which these data were collected).

Abbreviations: AD = atopic dermatitis; BSA = body surface area; EASI = Eczema Area and Severity Index;

IGA = Investigator Global Assessment; NRS = Numerical Rating Scale; POEM = Patient-Oriented Eczema Measure; TCI = topical calcineurin inhibitor; TCS = topical corticosteroid.

- a Achieving EASI-75 requires a ≥75% reduction in EASI scores from baseline to a later visit.
- b Pruritus NRS, Sleep-loss Score, TCS/TCI use, and Skin Pain NRS are only collected up to Week 52, not through the end of study (Week 100).

5. Study Design

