6.10. Prior and Concomitant Therapy

Medications will be classified into anatomical therapeutic chemical (ATC) drug classes using the latest version of the World Health Organization (WHO) drug dictionary. Medication start and stop dates will be compared to the date of first dose of treatment in Study KGAA to be classified as prior or concomitant.

Prior medications are those medications that start and stop prior to the date of first dose of study treatment in Study KGAA. *Concomitant medications* are those medications that start before, on, or after the first day of Study KGAA treatment and continue into the treatment period.

Prior medication and concomitant medication will be summarized by the treatment group for the mITT Population.

Specific AD treatment used during the Study KGAA treatment period will be presented by the treatment group for the mITT Population. This will include: topical AD treatment (including TCS, TCI, and crisaborole) and systemic AD treatment (including systemic corticosteroids, immunosuppressants, biologics, and phototherapy). The TCS will be presented by potency. A definition of rescue medications is provided in Appendix 2. For patients coming from parent Study KGAD, daily TCS/TCI use will continue to be collected via patient diary until Week 52 and will be summarized.

Flare

Disease flares will be assessed based on rescue therapy usage. Flare is defined as the initiation or intensification of rescue therapy. A summary of the percentage of patients rescued by visit will be provided.

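### The rescue rule in SAP Appendix 2 never checks the recorded indication, so listed drugs given for other diseases count as AD rescue and their start as a flare

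*SAP*

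**What the plan says.** SAP Section 6.10 plans summaries of AD treatment, topical and systemic, and sends the reader to Appendix 2 for the definition of rescue medication. It then states: "Flare is defined as the initiation or intensification of rescue therapy". It also promises the percentage of patients rescued at each visit.

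Appendix 2 sorts drugs under two headings, topical and systemic AD treatment. The entries below those headings are:

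- Topical steroids: "Topical Corticosteroids (TCS): ATC code is D07", with a topical or transdermal route. Topical calcineurin inhibitors and crisaborole go by preferred term.
- Systemic steroids: "Systemic Corticosteroids: ATC code is H02".
- Immunosuppressants: "ATC2 is L04 or Preferred terms of Abrocitinib or Ruxolitinib excluding Preferred terms mentioned in" the biologics entry.
- Biologics: "Biologics: Defined as following preferred terms", followed by a fixed list.
- Routes for these systemic classes: "Oral, Intra-Arterial, Intramuscular, Intraperitoneal, Intravenous, Subcutaneous, and Transdermal".
- Phototherapy: a search on the medication name, "then medical to manually review to confirm whether the medication in question is indeed" phototherapy or photochemotherapy.

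SAP Section 4, Table KGAA.4.1, lists among the other secondary endpoints: "Proportion of patients requiring AD concomitant treatment by visit".

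**The concern.** Steroids and immunosuppressants are used for many diseases besides AD. A rule that identifies the drug but not the reason for it cannot tell an oral steroid course for AD from one for asthma. Because flare has no clinical criterion and rests wholly on rescue, the same record also becomes a disease flare.

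At stake are the flare summary and the percentage rescued by visit. Both would mix AD control with use of the listed classes for other illnesses. Section 6.1.3 splits efficacy data by parent-study group, so if these summaries are shown that way, groups with different comorbidity could look different for reasons unrelated to AD.

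**Working it through.** No figure in either document depends on this rule, so there is none to reproduce. The check is a reading of each step, followed by an illustration.

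**Does any step test the indication?**

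| Class | How identified | Further condition | Indication tested? |
|---|---|---|---|
| Topical steroids | ATC D07 | topical or transdermal route | no |
| Calcineurin inhibitors, crisaborole | preferred term | topical or transdermal route | no |
| Systemic steroids | ATC H02 | seven listed routes | no |
| Immunosuppressants | ATC L04 or two preferred terms | seven listed routes; listed biologics removed | no |
| Biologics | list of preferred terms | seven listed routes | no |
| Phototherapy | name search | manual medical review | no: the review confirms the type of treatment |

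**Following one record through.** Take an oral H02 drug started for a disease other than AD. It meets the code and the route, so Appendix 2 makes it systemic AD treatment. Section 6.10 takes rescue from Appendix 2, so the patient is counted as rescued. The drug was newly started, so Section 6.10 also counts a flare. Nothing on that path removes the record.

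**Direction.** Every patient with AD-indicated use of a listed drug is counted whether or not non-AD use is also counted. Admitting non-AD use can therefore only add patients.

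**The secondary endpoint.** Tables KGAA.6.6 and KGAA.6.7 contain no row for AD concomitant treatment by visit. Section 6.10 with Appendix 2 is the nearest operational definition, but no sentence links the two.

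**Size, illustration only.** Let r be the true proportion with AD rescue and q the proportion using a listed class for another reason. Both are assumptions, taken as independent. Then

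apparent rescue = r + (1 − r) × q, and misclassified share = (apparent − r) / apparent.

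For r = 10% and q = 5%: 0.10 + 0.90 × 0.05 = 14.5%, and the share is 4.5 / 14.5 = 31%. The range is:

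| r | q = 2% | q = 5% | q = 10% |
|---|---|---|---|
| 5% | 6.9% (28% misclassified) | 9.75% (49%) | 14.5% (66%) |
| 10% | 11.8% (15%) | 14.5% (31%) | 19.0% (47%) |
| 20% | 21.6% (7%) | 24.0% (17%) | 28.0% (29%) |

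The table shows only that the error could be small or large. It does not estimate the error in this study.

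**The case against.** The strongest reply is that Appendix 2 never says a drug counts whatever its purpose. Its headings name AD treatment, so the codes can be read as class definitions applied to records already known to be for AD. The revision history says the appendix was added to follow the PSAP. Neither the PSAP nor the main KGAA protocol was available, so a filter in either cannot be excluded. The route list also keeps out inhaled, nasal and ocular steroids. Any over-count works against the drug, and an all-use rule is easy to reproduce.

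Much of this stands. The headings show the intent, and the route list narrows the problem. But the intent is not turned into a step, and neither Section 6.10 nor Appendix 2 points to a filter elsewhere. A programmer working from the SAP would count all use.

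Four stronger readings are tempting, and the documents do not support them:

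- *IGA and EASI response rates are distorted.* They are not. The SAP's efficacy estimands in Section 6.2.2 treat only treatment discontinuation as an intercurrent event.
- *Stable background topical steroid in patients from KGAD is counted as flare.* It is not, because Section 6.10 requires a start or a step-up. Such use can still enter the percentage rescued, since concomitant medication includes drugs begun earlier and continued into KGAA.
- *The secondary endpoint is certainly overstated.* That depends on a derivation the SAP does not state.
- *The phototherapy review is an existing blinded indication review.* The SAP does not call it blinded, and it does not look at the reason for use.

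**Conclusion.** The point holds as a minor defect in a stated programming rule. As written, listed-route H02 steroids, L04 agents and D07 topicals given for other diseases are classed as AD rescue, and starting or intensifying them counts as a flare. The flare and rescue-by-visit summaries can only be overstated by this. The AD concomitant treatment endpoint shares the fault if it is derived from Appendix 2.

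The size is unknown. A reader might infer a particular percentage inflation from the illustration, but neither document gives a rate of AD rescue or of non-AD use. The primary endpoint, discontinuation of treatment due to adverse events, is not affected. The SAP plans no statistical tests, so no inference changes.

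The conclusion assumes that no indication filter sits in the PSAP or the main protocol.

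**What to change.** In Appendix 2:

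1. Count a record as AD treatment or rescue only if its recorded indication is atopic dermatitis or its worsening. This assumes the medication form records an indication.
2. Send records with a missing or ambiguous indication to medical review done without sight of treatment assignment.
3. Keep the present all-use rule as a sensitivity summary.
4. For patients from KGAD, show continuing background topical use separately in the percentage-rescued summary. The flare definition needs no change here.
5. State whether the AD concomitant treatment endpoint is derived from Appendix 2.

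If the PSAP already contains the filter, a sentence in Appendix 2 citing it replaces items 1 and 2.

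The cost is one filter and a short review list. The filter may under-count where the indication is missing or miscoded; setting its result beside the all-use count shows how much the choice matters. SAP Version 3 was signed on 21 March 2025, and its revision history says it records analyses from a clinical study report approved on 22 January 2025. Revised summaries would therefore be supplementary and should be labelled post hoc.

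### Appendix 2 gives no rescue class to ruxolitinib recorded with route Topical and finds phototherapy only through 'photo' in the term, so the descriptive rescue summaries can miss such records

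*SAP*

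**What the plan says.** SAP Section 6.10 makes Appendix 2 the operative definition: "A definition of rescue medications is provided in Appendix 2". It builds flare on the same classes ("Flare is defined as the initiation or intensification of rescue therapy") and plans a by-visit output: "A summary of the percentage of patients rescued by visit will be provided".

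Appendix 2 has a topical and a systemic group.

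- **Topical.** "Route of topical treatments includes: Topical and Transdermal". There are three rules: topical corticosteroids by ATC code D07, calcineurin inhibitors by the preferred terms tacrolimus and pimecrolimus, and crisaborole by preferred term.
- **Systemic.** The routes are "Oral, Intra-Arterial, Intramuscular, Intraperitoneal, Intravenous, Subcutaneous, and Transdermal", with the qualification "This condition applies to the following categories except for phototherapies". The immunosuppressant rule reads "ATC2 is L04 or Preferred terms of Abrocitinib or Ruxolitinib excluding Preferred terms mentioned in" the biologics class. This is the only place where ruxolitinib is named.
- **Phototherapy.** The rule begins "Programming search of medication name (actual term or preferred term) contains" and gives one string, 'photo'. A medical reviewer then confirms whether each hit really is phototherapy or photochemotherapy.

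**The concern.** Appendix 2 names ruxolitinib as a rescue drug, but the route condition removes it when the route is Topical, and nothing in the topical group picks it up. Such a record would be in the database but in no rescue class.

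The phototherapy rule depends on one string. SAP Section 6.8.1 itself gives the abbreviation PUVA for photochemotherapy, and that abbreviation does not contain 'photo'. The medical review comes after the search, so it can remove a false hit but cannot recover a record that was never returned.

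At stake is whether the Section 6.10 summaries count every patient who used additional treatment for atopic dermatitis. A patient whose only rescue at a visit goes unclassified is shown as not rescued, and the start of that treatment is not seen as a flare.

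**Working it through.** The plan gives no rescue or flare figure, so there is nothing to reproduce. The check applies the Appendix 2 rules, as written, to constructed records. It shows how the rules behave and says nothing about how often such records occur.

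**Gap 1: ruxolitinib by route**

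| Preferred term | Route | Topical rules | Systemic rule | Result |
|---|---|---|---|---|
| Ruxolitinib | Oral | route not listed | term and route met | immunosuppressant |
| Ruxolitinib | Transdermal | route met, no rule names it | term and route met | immunosuppressant |
| Ruxolitinib | Topical | route met, no rule names it | term met, route fails | no class |
| Ruxolitinib, ATC2 assumed L04 | Topical | route met, no rule names it | code met, route fails | no class |
| Crisaborole | Topical | term and route met | not applicable | crisaborole |

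The fourth row shows that the ATC alternative in the immunosuppressant rule does not help, because the route condition covers that rule as well.

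**Gap 2: the phototherapy search**

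| Actual term | Preferred term (assumed) | 'photo' in either? | Result |
|---|---|---|---|
| PUVA | PUVA | no | not found |
| narrowband UVB | UVB | no | not found |
| UVB | Phototherapy | yes | found, sent to review |
| photochemotherapy (PUVA) | none | yes | found, sent to review |

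The third row matters: dictionary coding can rescue an abbreviated entry. Only a record with 'photo' in neither term is lost.

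**Direction.** A record that meets no class adds nobody to a rescue count. Omitting it can lower that count or leave it unchanged, the latter when the patient also has a classified rescue, such as a topical corticosteroid, at the same visit.

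**Reach.** SAP Section 6.2.1 defines the primary estimand by treatment discontinuation due to adverse events. Section 6.2.2 and Table KGAA.6.2 list only treatment discontinuation as an intercurrent event. Rescue use enters neither.

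**Check of the proposed search terms.** Matched as a substring, UVA returns rosuvastatin and fluvastatin; matched as a whole word it returns neither. Whole-word PUVA, UVA and UVB find 'PUVA', 'UVB' and 'NB-UVB' but miss 'NBUVB' and 'UVA1', so those two need their own entries. An entry such as 'Sunscreen UVA/UVB' is still returned and would be rejected at medical review.

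**The case against.** The strongest reply is that no effect is shown. No document says that topical ruxolitinib was available, permitted or used in this study, and no coded terms are given. Section 6.10 and Appendix 2 both describe topical treatment as corticosteroids, calcineurin inhibitors and crisaborole, so the narrow list is at least consistent. The SAP's revision history says that Appendix 2 was added to follow the program safety analysis plan. Neither that plan nor the main protocol's section on concomitant medication is supplied, so a deliberate program-wide choice cannot be excluded. No statistical tests are planned, and a missed medication record still appears in the general concomitant medication summary of Section 6.10.

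All of this stands as a limit on size. It does not close the gaps: the rules as written leave these records unclassified, and for ruxolitinib that sits oddly with naming the drug as rescue at all.

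A reader might infer more than the documents support:

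- **That reported rescue is too low on balance.** This is not shown. The H02 and L04 rules carry no indication condition, so systemic treatment given for another disease could be counted as rescue and pull the other way.
- **That phototherapy stored as a procedure is also lost.** The schedule that mentions procedures (protocol Section 2.14) belongs to Addendum (11), which this SAP never mentions. Nothing shows how the main study stored phototherapy.
- **That the secondary endpoint on need for concomitant atopic dermatitis treatment (SAP Table KGAA.4.1) is biased.** The SAP does not say that this endpoint is derived from the Appendix 2 classes.
- **That Transdermal appearing in both route lists makes the undercount worse.** A double classification would need an assumed ATC code and would change only the topical/systemic split, not whether the patient counts as rescued.

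**Conclusion.** Both gaps are real on the text of Appendix 2. Each missed record can only lower the rescue, flare and by-visit rescue summaries. The size is unknown and may be zero, and the documents support no percentage-point figure. An effect requires at least one ruxolitinib record with route Topical, or one phototherapy record without 'photo' in either term, in a patient with no other classified rescue at that visit. The primary endpoint and the IGA and EASI estimands are not touched. This is a low-cost improvement to a descriptive output and does not threaten the study's conclusions.

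**What to change.** 1. Query the existing medication data for preferred term Ruxolitinib with route Topical. Query also for PUVA, UVA, UVB, UVA1 and NBUVB as whole words, and for 'ultraviolet' and 'light therapy'.
2. In Appendix 2, add a topical rule for preferred term Ruxolitinib. Limiting it to route Topical leaves the present class of every other ruxolitinib record unchanged.
3. Add the listed terms to the phototherapy search, ahead of the existing medical review.
4. Align the wording with the program safety analysis plan.
5. Label the change post hoc: SAP Version 3 already documents analyses from a clinical study report approved on 22 Jan 2025.
6. Re-run the rescue and flare tables only if the query finds affected records. If it finds none, record that the gaps had no effect.

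The cost is one query, a few lines of appendix text, a small programming change on data already collected, and a few false hits for the medical reviewer to reject.
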